Complete eligibility checklist	x					
Complete Patient History Form: HX100	x					
Complete ASES Assessments: ASES100	x		х	x	х	х
Complete SANE Assessment: SANE100			x	x	x	х
Complete Constant Score Form: CST100	х		X**	x	х	х
Randomize Patient		х				
Record Operative Details: OP100		х				
Collect Radiographic Images (AP Int., AP Ext, and Axillary Views)			x	x	x	x
Protocol Deviation Form: PD100	As needed	As needed	As needed	As needed	As needed	As needed
Complete Adverse Event Form: AE100 and/or Serious Adverse Event SAE100	As needed	As needed	As needed	As needed	As needed	As needed
Complete patient Withdrawal Form: WD 100		As needed	As needed	As needed	As needed	As needed
Complete Device Revision/Removal: RR100			As needed	As needed	As needed	As needed

Each follow-up visit time point will be determined based on the date of surgery.

** At the 6 week interval, in order to protect the subscapularis repair, the strength and ROM sections are not to be completed by sites.

*** Annual follow up will continue until study closure or until the last enrolled patient reaches their 2 year follow up window.

BILATERAL PATIENTS

A patient undergoing staged bilateral surgery must sign a consent form **for each study procedure**. Each study shoulder will be randomized separately. Bilateral patients will be required to wait at least 9 months between procedures for the purposes of the study.

Patients with staged bilateral study implants will require two ASES, Constant Score, and SANE assessment forms to allow individual assessment of each operative side over the course of the study. Patients must be instructed to assess each shoulder individually, i.e., only record right-shoulder pain levels on the CRF for their right shoulder and only report left shoulder pain on the CRF for the left shoulder.

SCHEDULE OF FOLLOW-UP ASSESSMENTS

Post-operative clinical and radiographic evaluations will be performed according to the following schedule, with the associated visit windows:

- 6 weeks (± 2 weeks)
- 3 months (± 2 weeks)
- 1 year (± 2 months)
- 2 years (± 2 months)
- Annually thereafter* (± 2 months)
- * Until all patients reach the 2-year visit window or the study is closed

ASSESSMENT PARAMETERS AND METHODS

Pre-Operative Visit - Medical History, Demographic Data and Patient Eligibility

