It is possible that during the course of the study, certain changes may become desirable, although none are anticipated at this time. All changes to the investigation require prior approval from the investigator's Institutional Review Board (IRB) or Ethics Committee (EC) and if necessary, the FDA. Any other deviation from the stated protocol will be considered as such and will be reported accordingly. Since TSA is an elective procedure, it is not expected that treatment will require administration in an emergency setting, therefore all changes to the protocol require review and approval by the investigator's IRB prior to implementation.

RADIOGRAPHIC PROTOCOL

A detailed radiographic protocol is contained in Exhibit 3.

STATISTICAL ANALYSIS PLAN

This is a two-group, multi-center, randomized single blinded clinical trial to compare Total Shoulder Arthroplasty with Biomet's Comprehensive[®] Shoulder System with nano humeral component to another active intervention, a Total Shoulder Arthroplasty with Comprehensive[®] Shoulder System with mini stem component (abbreviations: Investigational vs. Control).

PRIMARY STATISTICAL HYPOTHESES AND DEFINITION OF STUDY SUCCESS

This study is designed to show that the Investigational device is non-inferior to the control device using three co-primary study endpoints. This will be shown using a closed testing method in which each of the primary endpoints specified below are compared using α =0.05. Study success requires that the Investigational group successfully demonstrate non-inferiority when compared to the Control group for all three of the individual primary endpoints, using the statistical methods described below. Because non-inferiority must be successfully shown for all three endpoints for study success, the type I error rate is preserved at 5% for the entire primary endpoint.¹

The individual non-inferiority hypotheses for each of these three tests are as follows:

Radiographic Success

The proportion of successful outcomes (i.e., patients meeting radiographic success criteria) in the Investigational group is non-inferior to the proportion of successful outcomes in the Control group using a 10% margin of non-inferiority. The test is based on the lower bound of a one-sided 95% confidence interval for the difference, Investigational minus Control, in proportions of success at 22+ months. A conclusion of non-inferiority is supported if the lower bound of the confidence interval is at least -0.10.

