Information on plausible values of the percentage of patients projected to be radiographic failures was found by looking in the literature to find plausible rates for each component of the radiographic failure definition. Subsidence and migration of the humeral component and progressive radiolucency around the humeral component have been reported at approximately 2% and 0%, respectively. Migration of the glenoid component and progressive lucency of the glenoid component have been reported at approximately 5% and 6%, respectively⁶. Because some overlap is to be expected, the overall Radiographic Success rate is estimated to be 93% for sample size calculation purposes.

Assumptions:

α = 0.05	Probability of Type I error
β = 0.10	Probability of Type II error: power = $1 - \beta$
$p_{C} = p_{I} = 0.93$	Estimated success rate for Control and Investigational groups
δ = 0.10	Non-inferiority Margin

⁶ Sperling,et al. "Radiographic assessment of ingrowth total shoulder arthroplasty." *JBJS.* November/December 2000, Vol 9 No. 6, p 507-513.

Resulting sample sizes (number of shoulders), not adjusted for attrition, are 112 Investigational vs. 112 Control (5% type I error rate, 90% power). The sample size was increased by 15% to allow for possible attrition. This gives a sample size of 264 total subjects (132 Investigational and 132 Control).

Absence of Revision/Removal/UADE

Non-inferiority sample size calculations were implemented in nQuery Advisor 7.0 software using a 1:1 ratio of Investigational to Control subjects. This software uses methodology as described in a text by Farrington and Manning⁷.

The sample size needed to obtain 90% power for testing for non-inferiority of the investigational device to the control device with regard to Absence of Revision/Removal/UADE was calculated as follows:

Definitions:

p_I : Proportion of shoulders in the Investigational treatment group without a

Revision/Removal/UADE

 p_C : Proportion of shoulders the Control treatment group without a Revision/Removal/UADE δ : Non-inferiority margin. Lower 95% confidence bound for difference in proportions of clinically successful subjects at 22+ months (Investigational – Control) must be greater than $-\delta$.

For a specified constant, $0 < \delta < 1$, the hypotheses of non-inferiority are:

$$H_0: p_I - p_C \le -\delta vs. \quad H_A: p_I - p_C > -\delta.$$

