Subjects who have been randomized to the Investigational or Control group in this study comprise the All Enrolled population. The co-primary endpoints will be analyzed for the All Enrolled population and the results will be compared to the primary analyses performed on the Analysis population to determine whether the results of this analysis are consistent for both populations. For patients in the All Enrolled Population who are missing data necessary for the determination of any of the co-primary endpoints at 22+ months, data will be imputed as described below in the section "Sensitivity Analyses."

ANALYSIS POPULATION

Subjects who have been randomized to the Investigational or Control group in this study and who have complete data for a primary endpoint collected per the protocol at 22+ months or who have had a revision or removal at or before 26 Months will be included in the Analysis Population. This is the population that will be used in the primary study analysis and determination of study success. Those subjects who are missing their primary endpoint at 22+ months will be included as part of the All Enrolled population described above. Subjects with protocol deviations will be analyzed on an individual basis to determine if they will be included in the Analysis Population.

MISSING DATA AND SENSITIVITY ANALYSES

Data will be considered "missing" for a given primary endpoint if this endpoint cannot be calculated or is not available for a subject in the All Enrolled population. If the subject has had a

device failure at any point on or prior to their 22+ month outcome, they will *not* be considered as missing data for the Absence of Revision/Removal/UADE endpoint, as this endpoint is cumulative. A subject who has had a revision or removal prior to two years will be considered a radiographic failure at the 22+ month time point for purposes of the primary analysis. When possible (i.e. the subject is seen by a study investigator in a non-emergency situation and collection of the data will not cause undue burden), ASES scores will be collected for these cases before the revision is performed in order to prevent these patients from missing knee scores in the primary efficacy analyses.

Sensitivity analyses will examine the sensitivity of the results to missing values of the primary outcomes using the following analyses:

Outcome Type	Analysis Description	
Binary	Tipping Point Analysis: Missing observations are replaced with	

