(Radiographic Success,	values until the lower limit of the 95% Confidence interval for the	
Absence of	difference in proportions is equal to the non-inferiority margin	
Revision/Removal))	(the tipping point). Graph will show which imputations of	
Kevision/Kemovaljj	success/failure for the missing values in the investigational and	
	control groups lead to a conclusion of inferiority, and which lead	
	to a conclusion of non-inferiority. Missing Values as Success: Imputation of missing values as	
	"success"	
	Missing Values as Failures: Imputation of missing values as	
	"failure"	
	lanure	
	Last Observation Carried Forward: Missing observations in	
	either group are imputed by taking the most recent outcome prior	
	to 24 months and using it in place of the missing 24-month	
	outcome.	
	2 Year In-Window Analysis : Only data collected within the 2-	
	year per-protocol visit window (22-26 months) are included in	
	this analysis.	
	Multiple Imputation: This method replaces each missing value	
	with a set of plausible values that represent the variability around	
	the choice of which value to impute.	
Continuous	Replace with Maximum: Imputation of missing ASES as "100"	
(ASES Score)		
	Replace with Minimum: Imputation of missing ASES as "0"	
	Last Observation Carried Forward: Missing observations in	
	either group are imputed by taking the most recent outcome prior	
	to 24 months and using it in place of the missing 24-month	
	outcome.	
	2 Year In-Window Analysis : Only data collected within the 2-	
	year per-protocol visit window (22-26 months) are included in	

this analysis.
Multiple Imputation: This method replaces each missing value
with a set of plausible values that represent the variability around
the choice of which value to impute.

In addition, in the event that one or more subjects receive the opposite treatment than the one they were randomized to receive, a sensitivity analysis will be done on patients "as randomized" to make sure it is consistent with the primary analysis ("as treated"). However, because randomization will be performed intra-operatively and the patient must be able to receive either treatment in order to be randomized, this situation is not expected to occur. Other sensitivity analyses will be conducted as needed (i.e. if the effect of missing data on a particular primary outcome is still unclear).

TESTS FOR INTERACTION

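### For Radiographic Success, an unrevised shoulder that already fails on its last early film counts as missing if it has no film from 22 months on, and three of the planned analyses can then score it a success.

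*Combined protocol and SAP*

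**What the plan says.** Radiographic Success is co-primary endpoint (c). The hypothesis concerns the difference "in proportions of success at 22+ months", tested "using a 10% margin of non-inferiority" with a one-sided 95% bound (Primary Statistical Hypotheses and Definition of Study Success).

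Under Radiographic Assessments and Table 1 (Screening and Follow-Up Clinical and Radiographic Exams), three views are taken at every postoperative visit. An independent central reviewer reads them against the 6-week film, so the 3-month and 1-year films can already show a failure as defined under Co-Primary Endpoints.

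The Analysis Population, which decides study success, takes subjects "who have complete data for a primary endpoint collected per the protocol at 22+ months" or with a revision or removal by 26 months. Missing Data and Sensitivity Analyses states that an earlier failure is not missing for Absence of Revision/Removal/UADE, because that endpoint is cumulative. For Radiographic Success the only carry-forward rule is: "A subject who has had a revision or removal prior to two years will be considered a radiographic failure".

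For shoulders with a missing binary endpoint, the same section lists a tipping-point analysis, "Missing Values as Success: Imputation of missing values as" success, the matching analysis as failure, LOCF, a 2-year in-window analysis and multiple imputation. The All Enrolled analysis draws on these imputations.

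**The concern.** Take an unrevised shoulder with 5 mm or more of humeral migration on its 1-year film and no film afterwards. Its last known status is failure, established by the trial's own central reader. Under the rules as written, its 22+ month endpoint is unavailable, so it leaves the primary radiographic analysis and enters the imputations as an unknown. Missing-as-success then contradicts a recorded reading. The tipping-point grid counts the shoulder among those that could be either, and nothing fixes its value in multiple imputation.

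The sensitivity analyses exist to show whether missing data could change the conclusion. If they can turn recorded failures into successes, their favourable end is more favourable than the data allow. This matters for this device: Risks/Benefits from the Investigational Device says that the stemless design may raise some implant-related risks and singles out loss of fixation with loosening or migration, which this endpoint measures.

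**Working it through.** **The plan's own figure.** Inputs from Sample Size Calculation, Radiographic Success: success 0.93 in both arms, margin 0.10, one-sided alpha 0.05, power 90%, 15% attrition.

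n = (1.645 + 1.282)² × 2 × 0.93 × 0.07 / 0.10² = 111.5, so 112 per arm; 112 / 0.85 = 131.8, so 132 per arm and 264 in total. Both figures reproduce.

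**Where the shoulder goes.**

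| Analysis | Unrevised, failing early film, no film from 22 months on |
|---|---|
| Primary (Analysis Population) | left out |
| Missing as success | success |
| Tipping point | either |
| Multiple imputation | either |
| LOCF | failure |
| Missing as failure | failure |
| 2-year in-window | left out |

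**Effect on missing-as-success (illustration).** The plan's Wald bound is difference − 1.645 × SE. The documents give no count of such shoulders, so the counts are assumed. Let 112 be observed and 20 missing per arm, with 104/112 control and 101/112 investigational successes.

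- All missing set to success: 121/132 v 124/132. Difference -0.0227, SE 0.0318, bound -0.0750: passes.
- Three of the 20 investigational shoulders held as failures: 118/132 v 124/132. Difference -0.0455, SE 0.0339, bound -0.1012: fails.
- Three held in each arm: 118/132 v 121/132. Difference -0.0227, SE 0.0360, bound -0.0820: passes.

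The reversal therefore needs an imbalance between arms as well as a result near the margin.

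**Possible effect on the primary analysis.** Let f be the true failure rate (0.17 v 0.07, exactly at the margin), e the share of failures visible by 1 year, r the share of visible failures that are revised (and so counted), and m the share of unrevised visible failures with no late film. All other shoulders have 15% missing. Per arm:

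- V = f·e·[r + (1 − r)(1 − m)]
- observed failure rate = [V + f(1 − e)·0.85] / [V + (1 − f·e)·0.85], with number observed = 132 × denominator
- P(declare non-inferiority) = Φ((0.10 − d)/SE − 1.645), where d is the difference in observed failure rates

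Worked case e = 0.75, r = 0, m = 0.50:

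- Investigational: V = 0.06375; (0.06375 + 0.036125)/(0.06375 + 0.741625) = 0.1240, on 106.3 shoulders.
- Control: V = 0.02625; (0.02625 + 0.014875)/(0.02625 + 0.805375) = 0.0495, on 109.8 shoulders.
- d = 0.0746, SE = 0.0381, and Φ(0.668 − 1.645) = 16.4%.

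| Visible by 1 year (e) | Revised (r) | m = 30% | m = 50% |
|---|---|---|---|
| 1/2 | 0 | 6.9% | 10.9% |
| 1/2 | 1/4 | 5.9% | 8.2% |
| 1/2 | 1/2 | 5.0% | 6.2% |
| 3/4 | 0 | 8.2% | 16.4% |
| 3/4 | 1/4 | 6.4% | 10.6% |
| 3/4 | 1/2 | 5.0% | 6.9% |

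With r = 0 and m = 15%, so that missingness is unrelated to failure, the result is 5.0%.

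**Scoring such dropouts as failures in the primary.** Suppose missingness is 15% throughout and none are revised. At a true failure rate of 7% and e = 1/2, the observed rate becomes (0.035 + 0.035 × 0.85)/(0.035 + 0.965 × 0.85) = 7.6%. Power at 7% v 7% falls from 90.2% to 88.4%, or to 87.5% at e = 3/4.

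**The case against.** The plan does not hide these shoulders. Missing-as-failure and LOCF both keep them as failures, missing-as-success is deliberately the optimistic extreme, the tipping-point graph shows both outcomes, and All Enrolled results must be compared with the primary. All of this stands, and it limits the point to the analyses that leave a recorded failure free. An optimistic extreme is informative only if it stays within what the data permit.

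The gap is also narrow. It needs an unrevised shoulder with no film at any time from 22 months on, while follow-up continues annually and a later film would supply the endpoint. The plan itself says that excessive loosening or migration of the nano component would require further surgery, so the worst cases are likely to be captured as revisions. Most of the failures assumed for planning are glenoid (about 5% and 6%, against 2% and 0% humeral), and the glenoid component is the same in both arms. These points stand and bear on size.

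The endpoint is status at 22+ months, and only the other binary endpoint is called cumulative. An early failing film is therefore strong evidence rather than the endpoint itself. That is a real, small cost of the fix. The radiographic protocol (Exhibit 3) is not in the documents, so a carry-forward rule there cannot be excluded.

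A reader might infer that the primary analysis is biased towards the nano device, or that such shoulders should be scored as failures in it. The documents support neither. They give no missingness rate for failing shoulders, no revised share and no difference between arms. Admitting missing shoulders only when they failed, while those with good early films stay out, is selection on outcome. It biases an otherwise unbiased comparison when missingness is unrelated to failure.

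**Conclusion.** The point holds for the imputation-based analyses. As written, they can score as a success a shoulder whose last central reading is a failure. In the illustration, three such shoulders, all investigational, are enough to reverse the missing-as-success result; with three in each arm it does not reverse.

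For the primary analysis no size can be fixed. With 30-50% of unrevised visible failures lacking a late film, type I error on this endpoint at the margin runs from about 5% (half of visible failures revised) to about 16% (none revised, three-quarters visible by 1 year). Every input to that range apart from the margin, the 7% planning rate, the 15% attrition and the 132 per arm is an assumption. It should be read as a range of possibilities and not as an estimate of error in this trial.

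**What to change.** Add to Missing Data and Sensitivity Analyses: in the All Enrolled, missing-as-success, tipping-point and multiple-imputation analyses of Radiographic Success, a shoulder without a 22+ month film whose last available post-baseline film meets a failure criterion listed under Co-Primary Endpoints is held as a failure; only shoulders whose status is unknown are imputed. Shoulders with a 22+ month film are scored on that film, as now. LOCF, missing-as-failure and the in-window analysis are unchanged.

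Leave the primary Analysis Population as it is. If the sponsor wants to see such shoulders counted as failures there, make that a pre-specified supportive analysis.

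The cost is about one sentence and no new data, since the films are already collected and centrally read. An earlier failing film is treated as lasting, and the optimistic sensitivity results become slightly less favourable.

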The Comprehensive® Shoulder System with nano humeral component addresses these issues by offering a minimally invasive humeral component that allows the surgeon to recreate the patient's natural humeral head version and inclination, while also allowing unobstructed access to the glenoid. The Comprehensive® Shoulder System with nano humeral component is an evolved design based on the Biomet TESS® shoulder that is currently marketed outside of the United States including Europe and Canada. The Comprehensive® Shoulder System with nano humeral component has a reverse morse taper locking mechanism that allows it to interface with Biomet's current offering of Comprehensive® shoulder components for enhanced flexibility in the surgical suite. The Comprehensive® nano also utilizes Biomet's proven PPS® Porous Plasma Spray technology for proximal fixation.

SECTION A: PURPOSE PURPOSE/OBJECTIVES

The purpose of this clinical investigation is to establish the safety and efficacy of the Comprehensive® Shoulder System with nano humeral component in Total Shoulder Arthroplasty. Safety and efficacy of the device will be measured by collection and analysis of the following data at the two-year or greater time point (22 months post-operative or longer):

- 1. American Shoulder and Elbow Surgeons (ASES) Score
- 2. Single Assessment Numeric Evaluation (SANE)
- 3. Constant Score
- 4. Radiographic assessment of osteolysis, radiolucencies, migration, and subsidence
- 5. Comparison of overall adverse event rates including rates of removal/revision and other serious adverse events.

Please refer to the Statistical Analysis Section for a description of the analyses that will be used.

RATIONALE FOR CURRENT STUDY

The current study is designed to determine the safety and efficacy of the Comprehensive[®] Shoulder System with nano humeral component implants (investigational) by measuring clinical, radiographic and safety outcomes when compared to the Comprehensive[®] Shoulder System with mini stem component (control) at the two-year or later follow-up time point.

The data collected as part of this study will be used to support Pre-Market Notification (U.S.) clearance of the Comprehensive[®] nano Humeral shoulder system and as such will be conducted according to all relevant FDA regulations for IDE clinical trials, sponsor and IRB requirements.

SECTION B: PROTOCOL OVERALL DESIGN

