- Patients with a life expectancy of less than three years.
- Patients diagnosed with severe shoulder instability
- Patients diagnosed with subscapularis incompetence
- Patients with active medico-legal activity regarding the index shoulder
- Patients known to be pregnant, planning to get pregnant, a prisoner, and/or alcohol or drug abuser
- Patients known to be involved in worker's compensation litigations regarding index shoulder
- Patients with known metal allergy
- Patients who refuse to sign the IRB approved consent form.
- Patients who are found intraoperatively to require a specific treatment and are unable to be randomized

• Patients, found at the time of intraoperative examination to have a single cyst >1cm in size or multiple cysts at implantation site

NOTE: Patients with a previous total shoulder replacement of the contralateral shoulder are eligible for participation in the study. However, the patient and surgeon must allow for at least 9 months between procedures.

PATIENT POPULATION

A study population of 132 investigational shoulders and 132 control shoulders undergoing primary total shoulder arthroplasty for any of the diagnoses in the Inclusion Criteria will be included in this study. All patients, regardless of sex, race, or geographic location must meet all the eligibility criteria. All patients must sign an Informed Consent to be enrolled into the study. The study requires that bilateral patients must be staged so, a separate Informed Consent must be completed for each operative side.

INSTITUTIONS

A maximum of 17 investigational sites will enroll patients into the study.

DURATION OF THE STUDY

Patient recruitment is expected to take place over a period of 24 months and all patients are to be followed annually until the last patient enrolled reaches the 2-year follow-up time point. Therefore, some patients will be evaluated for 3-5 years post-operatively or longer, depending on the length of enrollment.

STUDY DEFINITIONS AND GLOSSARY OF ABBREVIATIONS

Withdrawal: Patients who die or who formally withdraw their consent (in writing) to additional follow up. Patients who have had all components removed or humeral stem components removed.

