Absence of Revision/Removal/UADE

¹ Dmitrienko, Alex, et al. *Analysis of Clinical Trials Using SAS.* SAS Publishing, 2005, pp75-76.

The proportion of successful outcomes (i.e., patients not requiring a revision/removal of any device component or receiving a UADE during the course of the study) in the Investigational group is non-inferior to the proportion of successful outcomes in the Control group using a 10% margin of non-inferiority. The test is based on the lower bound of a one-sided 95% confidence interval for the difference, Investigational minus Control, in proportions of success at 22+ months. A conclusion of non-inferiority is supported if the lower bound of the confidence interval is at least -0.10.

American Shoulder and Elbow Surgeons Score

The mean American Shoulder and Elbow Surgeons (ASES) Score for the Investigational group is non-inferior to the mean ASES score for the Control group using a 9.5-point margin of noninferiority. This margin is based on an approximation that is sometimes used for the MCID based on the observation that for many patient-reported outcome measures, the MCID is about half the SD of change². This method is mentioned as well in an article by Singh et. al, where a half-standard deviation is mentioned as a generally accepted clinically significant benchmark³. Information about plausible values of the standard deviations ASES scores are available in an article by Angst, et. al.⁴ This article gives a standard deviation of postoperative ASES score for 142 subjects of 19.0 points, giving a half-standard-deviation of 9.5 points.

This test will be based on the lower bound of a one-sided 95% confidence interval for the difference, Investigational minus Control, in means at 22+ months. A conclusion of non-inferiority is supported if the lower bound of the confidence interval is at least -9.5 points.

RANDOMIZATION DETAILS

Study: Comprehensive® nano

² Murray et al. "The use of the Oxford hip and knee scores." *JBJS(Br)*. 2007; 89-B 1010-14.

³ Singh, Jasvinder et. al. "Challenges with health-related quality of life assessment in arthroplasty patients: Problems and solutions". *J Bone Joint Surg* 2010; 18:72-82.

⁴ Angst et. al. "Responsiveness in Shoulder Arthroplasty Outcome Instruments." Arthritis & Rheumatism (Arthritis Care & Research) Vol. 59, No. 3, March 15, 2008, pp 391–398

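### The time limits for the three co-primary endpoints are not reconciled: a revision at 24 to 26 months can leave a shoulder in the primary set with no defined radiographic result, and no rule picks among several 22+ month visits

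*Combined protocol and SAP*

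**What the plan says.** The plan sets time limits for the primary endpoints in several places.

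- **Primary time point.** Section A (Purpose/Objectives) defines it as "22 months post-operative or longer". The SAP's analysis-window table has a 2-year window of days 669-791 and an open window beyond day 791.
- **Entry to the primary set.** Under Analysis Population, subjects "who have had a revision or removal at or before 26 Months will be included in the Analysis Population".
- **Revision as radiographic failure.** Under Missing Data and Sensitivity Analyses, "A subject who has had a revision or removal prior to two years will be considered a radiographic failure".
- **Revision/Removal/UADE endpoint.** The hypothesis section defines success as "patients not requiring a revision/removal of any device component or receiving a UADE during the course of the study", then tests proportions at 22+ months. The missing-data section instead refers to a "device failure at any point on or prior to their 22+ month outcome".
- **Last observation carried forward (a sensitivity analysis).** It takes the latest outcome prior "to 24 months and using it in place of the missing 24-month" outcome.
- **Length of follow-up.** Under Duration of the Study, "all patients are to be followed annually until the last patient enrolled reaches the 2-year follow-up time point". Recruitment is expected to last 24 months.
- **Follow-up after revision.** Under Discontinuations and Revisions, follow-up ends when all components or the humeral stem are removed. It continues after any other partial revision.

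The restriction to 22-26 months appears only as a sensitivity analysis. No section says which visit supplies the primary value when a shoulder has more than one at 22+ months.

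**The concern.** All three co-primary endpoints must pass, so each needs one outcome per shoulder, fixed in advance. The stated limits leave three openings.

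1. The rule admitting revised shoulders runs to 26 months, while the rule making them radiographic failures stops at two years. A known device failure can fall between them and leave the radiographic comparison.
2. The revision endpoint has two possible cut-offs, which classify a late revision differently. If the whole study counts, shoulders also contribute different lengths of exposure.
3. A shoulder enrolled early can have 2-year, 3-year and possibly 4-year visits that all qualify. Choosing among them after the data are seen would affect both ASES and radiographic success.

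**Working it through.** **Step 1: the plan's own figures.** Inputs from the radiographic sample-size section: success 0.93 in both arms, margin 0.10, one-sided alpha 0.05, power 90%.

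- n = (1.645 + 1.282)² × 2 × 0.93 × 0.07 / 0.10² = 111.5, so 112 per arm, as stated.
- With 15% attrition, 112 / 0.85 = 131.8, so 132 per arm, as stated.
- At 30.4375 days per month, 22 months is 669.6 days and 26 months is 791.4 days. Days 669-791 are therefore the 22-26 month window. Two years is 730.5 days.

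**Step 2: the rules applied to cases**, reading two years literally as 24 months.

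| Case | In the primary set? | Outcome under the stated rules |
|---|---|---|
| Stem removed at 23 months, no 22+ month film | Yes | Radiographic failure |
| Stem removed at 25 months, no 22+ month film | Yes, by the 26-month clause | No failure rule applies and follow-up ends, so the radiographic endpoint is missing |
| Successful film at 23 months, revision at 25 months | Yes | Film says success; the plan does not say whether film or revision decides |
| Partial revision at 25 months, later film taken | Yes | The later film can supply a value; precedence is again unstated |
| Assessed at 24 months, revised at 30 months | Yes | Revision endpoint: failure over the course of the study, success up to the shoulder's own 22+ month outcome |

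**Step 3: shoulders that can have a second qualifying visit.** Let accrual be uniform over A months, and let the study close when the last shoulder is at c months. The share reaching a visit at v months is (A + c − v) / A. Uniform accrual is an assumption; A = 24 is the plan's figure.

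- Nominal dates (c = 24, v = 36): (24 + 24 − 36) / 24 = 50%.
- Low end of the visit windows (c = 22, v = 38): 8 / 24 = 33%.
- High end (c = 26, v = 34): 16 / 24 = 67%.
- Accrual rising linearly, nominal dates: (12/24)² = 25%. Falling linearly: 1 − (12/24)² = 75%.
- Accrual over 36 months, nominal dates: 24 / 36 = 67%.

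These shares are before attrition.

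**Step 4: expected revisions at 24-26 months.** The planning rate is 2.0% at a minimum of 2 years. Assume a constant hazard:

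- h = −ln(0.98) / 24 = 0.000842 per month.
- P(24-26 months) = exp(−24h) − exp(−26h) = 0.00165.
- Expected number: 264 × 0.00165 = 0.44.
- Chance of at least one: 1 − (1 − 0.00165)²⁶⁴ = 35%.
- With an assumed 5% rate instead, the expected number is about 1.1.

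**Step 5: effect of one shoulder on the radiographic test.** The Wald lower bound is (p_I − p_C) − 1.645 × √[p_I(1 − p_I)/n_I + p_C(1 − p_C)/n_C], and it must be at least −0.10.

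| Failures, Investigational vs Control | Lower bound |
|---|---|
| 8/112 vs 8/112 (planning rate) | −0.057 |
| 9/113 vs 8/112 (one more shoulder, counted as failure) | −0.066 |
| 12/112 vs 8/112 | −0.0983, passes |
| 13/112 vs 8/112 | −0.1085, fails |
| 12/111 vs 8/112 (one of those 13 Investigational failures drops out) | −0.0995, passes |
| 12/112 vs 7/111 (12 vs 8, but one Control failure drops out) | −0.1053, fails |

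At the planning rates one shoulder does not bring the bound near −0.10. Near the margin one shoulder can decide the result, and the direction depends on its arm.

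**The case against.** Several points on the other side stand.

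- A reader might infer that every shoulder revised at 24-26 months lacks a radiographic result. The documents do not support that. The 2-year window opens at day 669, so many will already have a film, and a partial revision that leaves the stem in place stays in follow-up.
- The two-year wording could mean before the 2-year visit. A stem removal at 25 months with no 2-year film would then be a failure. That reading is possible but not stated, and it still leaves open a shoulder filmed at 23 months and revised at 25.
- A reader might infer that lost revisions help the investigational device. The rules are the same in both arms, and Step 5 shows the effect in either direction. The revision also remains a failure on its own cumulative co-primary endpoint.
- A missing radiographic result is covered by the All Enrolled analysis, the tipping-point analysis, imputation as failure and multiple imputation.
- The whole-study count is only one reading of the revision endpoint, because the same paragraph tests proportions at 22+ months. Even on that reading, 1:1 randomisation blocked by site should roughly balance exposure between arms.
- The 24-month carry-forward rule belongs to a sensitivity analysis and is not a primary horizon.
- The 22-26 month in-window analysis would expose dependence on later visits. The radiographic protocol (Exhibit 3) is not available here.

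These points limit the size of the problem. The sensitivity analyses do not define the primary analysis, and none of them says which visit or which cut-off it uses.

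**Conclusion.** The point holds as a conflict between stated rules, with small expected numerical effect from the 24-26 month gap. The clear gap is a humeral stem or full removal in that interval with no earlier 22+ month film. About 0.4 revisions of any kind are expected in the interval among 264 shoulders, assuming a constant hazard at the 2.0% planning rate, and only some would lack a film. The radiographic result would change only near the margin, and in either direction.

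The two cut-offs for the revision endpoint and the absence of a visit-selection rule do not depend on that rare event. The second could touch a sizeable share of shoulders: about 50% under assumed uniform 24-month accrual, 33% to 67% across visit windows, before attrition. That is the share able to have a second qualifying visit. The documents give no basis for estimating how often two visits would disagree, so they do not support a claim that the choice of visit would change the conclusion.

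**What to change.** Three changes, settled before outcome data are examined:

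1. Count any revision or removal through 26 months (day 791) as a radiographic failure, whether or not an earlier film exists. This matches the existing Analysis Population rule.
2. Reconcile the two statements of the revision endpoint to one cut-off, for example day 791. Report all later revisions, UADEs, fractures, dislocations and dissociations in the safety tables. Show later revisions in the Kaplan-Meier analysis as well; that analysis covers time to revision only, so it cannot carry the other events.
3. Take primary ASES and radiographic values from the visit in days 669-791, and use the earliest later visit only if that one is missing. Keep the existing provision for ASES scores collected before a revision, which a strict day-669 limit would otherwise discard.

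The cost is small: SAP and protocol wording with the usual IRB approval and, where applicable, FDA approval, and no extra patients or visits. The trade-off is that events after day 791 leave the primary test of the revision endpoint.
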